### 3      **Investigational Plan**

#### 3.1      **Overview and study design**

This pharmacodynamic/phase 0 trial is designed as a randomized two-arm (LDE225 vs. observation groups) open-label prospective clinical trial in men with localized high-risk prostate cancer undergoing radical prostatectomy.

Activation of the Hedgehog pathway is most reliably indicated by increased expression of the *GLI1* transcription factor. Quantitative RT-PCR (qRT-PCR) provides the most reliable means to assess changes in *GLI1* expression upon exposure to drug and will be used as our primary readout. Our intent will be to examine the fold change in *GLI1* expression in each man following exposure to drug (comparing pre-operative needle biopsy tissue to surgical tissue obtained from the same man's prostatectomy specimen). Because the effects of surgery and fluctuations in hedgehog signaling in the prostate are unknown, *GLI1* expression will also be compared between biopsies and prostatectomy specimens for men without drug exposure. As treatment with LDE225 may alter the gene expression of other Hedgehog pathway members and affect separate signaling pathways, as an exploratory goal, we will perform genome-wide expression analysis using the GeneChip Human Exon 1.0ST Array (Affymetrix) and will confirm fluctuations in selected genes of interest.

High-risk patients will be identified based on their core-needle biopsy features, PSA levels, and clinical stage. Eligible men (NCCN high-risk (Gleason sum  $\geq 8$ , or PSA  $>20$  or clinical stage  $\geq T3$  with no evidence of metastatic disease) will undergo a repeat prostate biopsy at Johns Hopkins with multiple (up to 12) cores taken from the area of their primary lesion. This tissue will be frozen fresh and used for analysis of *Gli1* mRNA expression and array analysis as well as mounted for pathological analysis and IHC analysis of proliferation (Ki-67) and apoptosis (cleaved caspase-3) markers.

[figure not shown]
After obtaining baseline laboratory and clinical values (including an ECG, PSA, hematologic, and renal and hepatic panels), men will receive oral LDE225 800 mg/day or observation daily for 4 weeks ( $\pm 3$  days) prior to prostatectomy. Patients will have a clinical visit and an ECG and laboratory testing will be performed at 2 weeks and then again at 4 weeks, including a 4-week pre-prostatectomy measurement of PSA and a blood sample to determine plasma LDE225 levels by LC-MS/MS. Previous studies using other oral Hedgehog inhibitors indicate that 4 weeks will allow time for steady-state levels of drug in the plasma and for inhibition of *Gli1* expression ([LoRusso et al. 2011](#)).

Men will undergo radical prostatectomy (with bilateral pelvic lymphadenectomy as appropriate), at which point two 250-mg biopsies of prostate tissue will be obtained, frozen and stored for analysis (including *Gli1* expression, genome-wide expression analysis, intra-prostatic LDE225 levels, Ki-67, and cleaved caspase-3) with the remainder of the prostate tissue then being formalin-fixed paraffin-embedded (FFPE) and cross-sectioned for analysis as per our standard institutional procedures.

Relative fold-changes in mRNA expression of *Gli1* will be determined by first normalizing input amounts of the preoperative biopsy and prostatectomy biopsies to the housekeeping gene *HPRT1*. IHC comparisons between diagnostic biopsy specimens and prostatectomy specimens will be made by calculating immunoreactivity scores (staining intensity  $\times$  percentage cell involvement).

Protocol Version 3: October 6, 2015

All men will receive routine post-operative care, and in addition will have ultrasensitive PSA testing at 1 and 2 months post-op followed by standard PSA testing at the 3 month visit.

Study Schema

### 3.1.1 Investigational treatment

The investigational study drug used in this trial is LDE225, which is supplied as oral capsules.

### 3.1.2 Treatment arms

This will be a randomized 2-arm trial. Arm 1 will receive LDE225 by mouth 800 mg daily for 4 weeks ( $\pm 3$  days); Arm 2 will receive no treatment (observation) prior to prostatectomy.

### 3.1.3 Treatment duration

Patients will continue on LDE225 therapy for 4 weeks ( $\pm 3$  days) in Arm 1, or until they experience a treatment toxicity requiring discontinuation.

### **3.1.4 Treatment assignment/randomization**

Patients will be randomized (1:1) to treatment with LDE225 or observation, with a total sample size of 22 patients (*i.e.* 11 per group).

## **3.2 Rationale for the study design**

Discrepancies between preclinical data and clinical observations highlight the need to carry out pharmacodynamic studies of promising cellular pathway inhibitors before conducting large-scale clinical trials for efficacy. While pre-clinical data suggests a role for LDE225 in the inhibition of prostate cancer progression, no clinical study exists which confirms the ability of LDE225 to suppress the Hedgehog pathway in prostate cancer. For this reason, we believe that a phase 0 (pharmacodynamic) trial would be instrumental in determining whether further larger clinical studies should be carried out with LDE225 in prostate cancer.

From a tissue acquisition perspective, a pre-surgical trial involving biopsy tissue collection and tissue at prostatectomy would be ideal for determining whether LDE225 has effects on its *in vivo* target and additionally to measure genome-wide alterations caused by drug exposure.

Based on our pre-clinical data (and that of other groups) we believe that men with NCCN high risk prostate cancer are the best candidates for this trial due to relative enrichment in baseline Hedgehog pathway activation in this subgroup (Ross et al. 2011, Tzelepi et al. 2011, Chen et al. 2010, Kim et al. 2011). Because the temporal variability of Hedgehog pathway activity and the effects of surgical treatment on pathway activation are largely unknown, we believe that a control/observation arm is critical to the study.

## **4 Population and Eligibility Criteria**

**Target Population.** This study will include men age 18 or older diagnosed with NCCN high-risk (Gleason sum  $\geq 8$ , or PSA  $>20$ , or clinical stage  $\geq T3$ ) prostate cancer who are candidates for radical retropubic prostatectomy.

### **4.1 Inclusion criteria**

Patients must meet **all** of the following criteria:

1. Provide written informed consent prior to any screening procedures.
2. Age 18 years or older.
3. Histologically-documented prostatic adenocarcinoma in  $\geq 2$  cores
4. ECOG performance status  $\leq 2$
5. Localized prostate cancer with *at least one* of the following NCCN high-risk features:
  - Gleason sum  $\geq 8$
  - PSA  $>20$  ng/mL
  - Clinical stage  $\geq T3$
6. Must be a candidate for radical prostatectomy
7. No evidence of known metastatic disease (M0 or Mx allowed)
8. Adequate bone marrow, liver and renal function as specified below:

- Absolute neutrophil count (ANC)  $\geq 1.5 \times 10^9/L$
- Hemoglobin (Hgb)  $\geq 9.0 \text{ g/dL}$
- Platelets  $\geq 100 \times 10^9/L$
- Serum total bilirubin  $\leq 1.5 \times \text{ULN}$  (upper limit of normal)
- AST and ALT  $\leq 2.5 \times \text{ULN}$
- Plasma creatine phosphokinase (CK)  $< 1.5 \times \text{ULN}$ , if known
- Serum creatinine  $\leq 1.5 \times \text{ULN}$  [or 24-hour creatinine clearance  $\geq 50 \text{ ml/min}$ ]

9. Patient is able to swallow and retain oral medications

## 4.2 Exclusion criteria

Patients must not meet **any** of the following criteria:

1. Patients who have had major surgery within 4 weeks of enrollment.
2. Patients with concurrent uncontrolled medical conditions that may interfere with their participation in the study.
3. Patients unable to take oral drugs (*e.g.* lack of physical integrity of the upper GI tract or known malabsorption syndromes).
4. Patients who have previously been treated with LDE225 or other Hh pathway inhibitors.
5. Patients who have neuromuscular or muscular disorders (*e.g.* inflammatory myopathies, muscular dystrophy, amyotrophic lateral sclerosis and spinal muscular atrophy) or are on concomitant treatment with drugs that are known to cause rhabdomyolysis (such as statins and fibrates), and that cannot be discontinued at least 2 weeks prior to starting LDE225. If it is essential that the patient stays on a statin for hyperlipidemia, only *pravastatin* may be used with extra caution. Patients should not plan to embark on a new strenuous exercise regimen after initiation of study treatment. (NB: Muscular activities, such as strenuous exercise, that can result in significant increases in plasma CK levels should be avoided whilst on LDE225 treatment).
6. Patients who have taken part in an experimental drug study within 4 weeks or 5 half-lives (whichever is longer) of initiating treatment with LDE225.
7. Patients who are receiving other anti-neoplastic therapy (*e.g.* chemotherapy, targeted therapy or radiotherapy) concurrently or within 2 weeks of starting LDE225.
8. Patients taking moderate/strong inhibitors or inducers of CYP3A4/5 or drugs metabolized by CYP2B6 or CYP2C9 that have narrow therapeutic index, and that cannot be discontinued before starting treatment with LDE225. Medications that are strong CYP3A4/5 inhibitors should be discontinued for at least 7 days and strong CYP3A5 inducers for at least 2 weeks prior to starting treatment with LDE225.
9. No concurrent use of statins (except for pravastatin, *if absolutely necessary*)
10. No concurrent warfarin or Coumadin-derivatives
11. Impaired cardiac function or significant heart disease, including any one of the following:
  - Angina pectoris within 3 months
  - Acute myocardial infarction within 3 months
  - QTc  $>450 \text{ msec}$  on the screening ECG
  - A past medical history of clinically significant ECG abnormalities or a family history of prolonged QT-interval syndrome

- Other clinically significant heart disease (e.g. heart failure, uncontrolled/labile hypertension, or history of poor compliance with an antihypertensive regimen)

12. Patients who are not willing to apply highly effective contraception during the study and through the duration of LDE225 treatment.

- **Male patients** must use highly effective (double barrier) methods of contraception (e.g., spermicidal gel plus condom) for the entire duration of the study, and continuing using contraception and refrain from fathering a child for 6 months following the last dose of the study drug. A condom is also required to be used by vasectomized men as well as during intercourse with a male partner in order to prevent delivery of the study treatment via seminal fluid. Sexually active males must be willing to use a condom during intercourse while taking the study drug and for 6 months after stopping investigational medications and agree not to father a child during this period.

13. Patients unwilling or unable to comply with the research protocol.

## 5 Treatment

### 5.1 Treating the patient

The treating investigator needs to instruct the patient to take the study drug as per protocol. All dosages prescribed and dispensed to the patient and any dose change or interruption must be recorded in the dosage administration record (CRF) as appropriate.

#### 5.1.1 Administration

**Table Treatment and schedule**

Study treatments	Pharmaceutical form and route of administration	Dose	Frequency and/or regimen
LDE225	Capsules (200 mg) for oral use	800 mg	Daily

LDE225 will be administered orally, on a continuous once-daily schedule, at a dose of 800 mg. Participating patients will receive flat doses on mg/day basis and not according to their body weight or body surface area. LDE225 is supplied as 200-mg hard gelatin capsules in bottles and must be stored at 2-8°C/ 35.6-46.3°F. **Patients will receive 4 capsules of LDE225 daily (= 800 mg/day).**

#### 5.1.2 Dosing and treatment schedule

Patients will be dosed at 800 mg of LDE225 daily. Hard gelatin capsules at 200 mg are available (4 capsules will be taken all at one time). Dose escalation will *not* be allowed.

LDE225 should be taken as follows:

- Men should be instructed to take their daily dose at approximately the same time each day
- On days where PK samples need to be collected prior to taking study drug, that day's dose should be taken in the clinic (study site)
- Each daily dose of LDE225 should be taken with a glass of water and consumed over as short a time as possible (e.g. 1 capsule every 2 minutes)

Protocol Version 3: October 6, 2015

- Patients should be instructed to swallow capsules whole and to *not chew or open* capsules
- Each daily dose of LDE225 (including days which involve PK blood sampling) should be taken **2 hours after** a light breakfast (e.g., consisting of juice, toast and jam). Food intake should be avoided for at least 1 hour after study drug administration
- Patients must avoid grapefruit, pomegranate, star fruit and Seville (sour) oranges during the entire study. The juices and products containing these fruits may also be avoided.
- If vomiting occurs during the course of the treatment, then no re-dosing of the patient is allowed before the next scheduled dose the following day
- If the patient forgets to take his daily morning dose, then he should take LDE225 within 6 hours after the missed dose. If more than 6 hours have passed, then that day's dose should be omitted and the patient should continue treatment with the next scheduled dose
- Patients should inform the investigational site staff of any missed or delayed doses

### 5.1.3 Dose modification and dose delay

Investigators should follow the guidelines *described below* for the modification of LDE225 treatment. Any plan to deviate from these guidelines in view of the patient safety must be previously discussed with Novartis unless there is an urgent need for action.

All dose modifications should be based on the worst preceding toxicity. If study treatment is being held due to toxicity, scheduled visits and all assessments should continue to occur except the dosing of the study drug. Treatment related toxicities are adverse events that are possibly, probably or definitely related to the study drug.

Any grade 3 or grade 4 toxicities will result in discontinuation of the study drug. Men with prolonged grade 2 toxicity will receive a reduced dose of the study drug at 400mg. If the grade 2 toxicitiy continues on the reduced dose then the dose level will be reduced again to 200mg. A maximum of two dose-reduction steps will be allowed (see [Table below](#)), after which the patient will be discontinued from study treatment.

For patients who undergo dose interruptions (delays), if the same toxicity returns after re-initiation of treatment, regardless of duration, the second re-initiation must resume at a lower dose. If the patient requires a dose interruption of >7 days from the previous dose, then the patient must be discontinued from study treatment although he may still undergo prostatectomy. Patients who discontinue the treatment due to an adverse event or an abnormal laboratory value must be followed until resolution or stabilization of the event.

All dose changes or interruptions must be recorded in the dosage administration record (CRF) as appropriate.

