**Table Dose reductions for LDE225**

Dose reduction*			
	Starting dose level	Dose level -1	Dose level -2
LDE225 dose (mg QD)	800	400	200

\*Dose reduction should be based on the worst toxicity demonstrated.

Detailed indications and instructions for dose-modifications are shown below in Table 5-3. Different dose modifications are dependent on the type and severity of the toxicity, as shown in Table 5-3.

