**Table 5-1 Recommended Dose Modifications and Dose Delays for suspected treatment-related toxicities**

Recommended dose modifications for LDE225**	
Worst toxicity CTCAE grade* (value)	During a cycle of therapy
Hematologic	
Neutropenia (ANC)	
Grade 1 (ANC < LLN - 1500/mm  )	Maintain dose level
Grade 2 (ANC < 1500 - 1000/mm  )	Reduce dose to 400mg. If resolved in $\leq$ 7 days then maintain dose level. If not resolved in $\leq$ then decrease level to 200mg
Grade 3 or 4 (ANC < 1000 - 500/mm  or < 500/mm  )	
 
Discontinuation of study drug
 

Thrombocytopenia (PLT)	
Grade 1 (PLT < LLN - 75,000/mm  )	Maintain dose level
Grade 2 (PLT < 75,000 - 50,000/mm  )	Reduce dose to 400mg. If resolved in $\leq$ 7 days then maintain dose level. If not resolved in $\leq$ then decrease level to 200mg
Grade 3 or 4 (PLT < 50,000 - 25,000/mm  or < 25,000/mm  )	
 
Discontinuation of study drug
 

Febrile Neutropenia	
Febrile neutropenia (ANC < $1.0 \times 10^9$ /L, fever $\geq$ 38.5°C)	Omit dose until resolved, then decrease dose by 1 step
Muscle Toxicity	
Elevated creatine phosphokinase (CK)	
Asymptomatic (no new-onset muscle pain/spasm or worsening of pre-existing muscle pain/spasm) CTCAE grade 1 or 2 CK elevation	
 
For CTCAE grade 1 CK elevation, continue treatment on same dose and continue monitoring as per schedule of assessments
 
For sites in France: For treatment-emergent CTCAE grade 1 CK elevation, continue treatment on same dose. CK should be measured weekly until CK returns to normal for baseline value.
 
For CTCAE grade 2 CK elevation, collect blood sample for PK and consider performing a muscle biopsy; continue on same dose level of LDE225. CK should be measured weekly until resolution to <math>\leq</math> grade 1.
 

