Symptomatic (new-onset or worsening of pre-existing muscle pain/spasm) with CTCAE grade 1 or 2 CK elevation	
 
For CTCAE grade 1 CK with muscle pain/spasm <math>\geq</math> CTCAE grade 1, continue treatment at same dose and measure CK weekly until CK returns to normal or baseline value or muscle pain/spasm resolves
 
For CTCAE grade 2 CK with muscle pain/spasm <math>\geq</math> CTCAE grade 1, collect blood sample for PK and continue treatment at same dose level of LDE225. CK should be measured weekly until CK is <math>\leq</math> CTCAE grade 1
 

Recommended dose modifications for LDE225**	
Worst toxicity CTCAE grade* (value)	During a cycle of therapy
CTCAE grade 3 or 4 CK elevation (with or without muscle pain/spasm)	
 
Discontinuation of study drug
 

Muscle pain/spasm (new onset or worsening of pre-existing muscle pain/spasm)	
 
For CTCAE grade 1 muscle pain/spasm, continue treatment on the same dose and planned assessments
 
For CTCAE <math>\geq</math> grade 2 muscle pain/spasm, measure CK weekly until muscle pain resolves to <math>\leq</math> grade 1. If CK is elevated, follow guidance for CK elevation as described above. Continue treatment with LDE225
 
For new-onset CTCAE grade 3 muscle pain/spasm, study drug will be discontinued
 

Renal	
Serum creatinine	
Serum creatinine $<1.5 \times$ ULN	Maintain dose level
Serum creatinine 1.5-3 $\times$ ULN	Omit dose until resolved to $\leq$ grade 1, then: 
 
If resolved in <math>\leq</math> 7 days, then maintain dose level
 
If resolved in <math>></math> 7 days, then decrease dose by 1 step (consider checking serum CK, if not already done)
 

Grade 3 Serum creatinine $> 3.0 - 6.0 \times$ ULN	Discontinuation of study drug
Grade 4 Serum creatinine $> 6.0 \times$ ULN	Discontinuation of study drug
Hepatic	
Bilirubin	
Total bilirubin $<1.5 \times$ ULN	Maintain dose level
Total bilirubin 1.5-3 $\times$ ULN	Omit dose until resolved to $\leq$ grade 1, then: 
 
If resolved in <math>\leq</math> 7 days, then maintain dose level
 
If resolved in <math>></math> 7 days, then decrease by 1 step
 

Grade 3 Total bilirubin $> 3.0 - 10.0 \times$ ULN	Discontinuation of study drug

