Grade 4 Total bilirubin $> 10.0 \times$ ULN	Discontinuation of study drug
AST or ALT	
Grade 1 ( $>$ ULN - 3.0 $\times$ ULN)	Maintain dose level
Grade 2 ( $>$ 3.0 - 5.0 $\times$ ULN)	Maintain dose level
Grade 3 ( $>$ 5.0 - 20.0 $\times$ ULN)	
 
Discontinuation of study drug
 

Grade 4 ( $>$ 20.0 $\times$ ULN)	Discontinuation of study drug

Recommended dose modifications for LDE225**	
Worst toxicity CTCAE grade* (value)	During a cycle of therapy
Cardiac	
Cardiac - prolonged QTc interval ≥ grade 3 (QTc >500 msec or >60 ms from baseline on at least 2 separate ECGs taken within 1 hour)	
First Occurrence:
 
 
• Omit dose
 
• Perform an analysis of serum potassium and magnesium, and if below lower limit of normal, correct with supplements to within normal limits. Concomitant medication usage must be reviewed.
 
• Perform a repeat ECG within one hour of the first QTc >500 ms
 
• If QTc remains > 500 ms, repeat ECG as clinically indicated but at least once a day until the QTc returns to <480 ms.
 
• Once QTc prolongation has resolved, study treatment may be restarted at a reduced dose level
 
 
Second Occurrence:
 
 
• discontinue patient from further study treatment
 

Cardiac, general	
Grade 1 or 2	Maintain dose level
Grade 3	Discontinuation of study drug
Grade 4	Discontinuation of study drug
Other adverse events**	
Grade 1 or 2	Maintain dose level
Grade 3	Discontinuation of study drug
Grade 4	Discontinuation of study drug
All dose modifications should be based on the worst preceding toxicity. Treatment related toxicities are adverse events that are possibly, probably or definitely related to the study drug.	
If the dose-limiting toxicity recurs in a patient following 2 dose reductions, then further therapy with LDE225 will not be continued.	
If a patient requires a dose interruption of > 21 days from the intended day of the next scheduled dose because of an LDE225-related toxicity, then the patient must be discontinued from the study.	
*Common Toxicity Criteria for Adverse Events (CTCAE Version 4.0).	

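### Section 5.1.3 and Table 5-1 give different dose instructions for the same grade 2 toxicity, and nothing says which one governs

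*Combined protocol and SAP*

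**What the plan says.** Section 5.1.3 presents its content as guidelines that investigators should follow; planned departures go to the drug supplier beforehand unless action is urgent. For grade 2 events it says "Men with prolonged grade 2 toxicity will receive a reduced dose of the study drug at 400mg". If the toxicity "continues on the reduced dose then the dose level will be reduced again to 200mg". Neither sentence names a toxicity, and how long an event must last to count as prolonged is not stated. The reader is then sent onward: "Different dose modifications are dependent on the type and severity of the toxicity, as shown in Table 5-3". The document shows no Table 5-3; the detailed table that follows is headed Table 5-1.

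Table 5-1 has its own grade 2 instructions:

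- CK elevation without symptoms: "continue on same dose level of LDE225. CK should be measured weekly until resolution to" grade 1 or lower.
- CK elevation with symptoms: "collect blood sample for PK and continue treatment at same dose level of LDE225", again with weekly CK until grade 1 or lower.
- Muscle pain or spasm: weekly CK, the CK guidance if CK is raised, and treatment continues.
- Neutropenia and thrombocytopenia: "Reduce dose to 400mg", with no condition on duration.
- Creatinine and bilirubin at 1.5-3 x ULN: hold, then resume at the same level or one step lower according to a 7-day limit.
- AST/ALT, general cardiac events and all other adverse events: "Maintain dose level", with nothing on duration.

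**The concern.** An investigator cannot work from both passages. The text makes the reduction depend on persistence, whatever the toxicity. The table makes it depend on the type of toxicity, and for CK it keeps the dose until the event resolves. With no length for a prolonged event and no order of precedence, two investigators acting in good faith could treat the same event differently.

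Consistent handling of patients is at stake first. The second issue is what the treated arm received. The primary endpoint compares Gli1 at prostatectomy with Gli1 at biopsy after about 4 weeks on drug, in an arm of 11 men. If the dose during that period depends on which passage was read, the arm mixes dose histories for reasons unrelated to the patients. Section 8.1 does not say how dose-reduced men are to be described or handled in that comparison.

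**Working it through.** **The plan's own figure.** The arm size reproduces and is not in question. Section 8.1 gives 10% versus 70%, two-sided alpha 0.10 and power 80%. With mean rate 0.40, n = [1.645 x sqrt(2 x 0.40 x 0.60) + 0.842 x sqrt(0.10 x 0.90 + 0.70 x 0.30)]^2 / 0.60^2 = (1.140 + 0.461)^2 / 0.36 = 7.1. The continuity correction gives (7.1/4) x [1 + sqrt(1 + 4/(7.1 x 0.60))]^2 = 10.2, rounded up to 11 per arm.

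**The passages side by side.** Ten rows of Table 5-1 cover a grade 2 event or the 1.5-3 x ULN band. The two ULN rows carry no grade label but sit directly below grade 3.

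| Table 5-1 rows | Table instruction | Section 5.1.3 instruction | Conflict |
|---|---|---|---|
| CK, asymptomatic and symptomatic (2) | Same dose, weekly CK until grade 1 or lower | 400 mg if prolonged, then 200 mg | Clear |
| Neutropenia, thrombocytopenia (2) | 400 mg at onset | 400 mg only if prolonged | Different trigger |
| Creatinine, bilirubin (2) | Hold first, 7-day limit | 400 mg if prolonged; no hold | Different action |
| Muscle pain/spasm (1) | Continue treatment | 400 mg if prolonged, then 200 mg | Yes, but no dose level is named |
| AST/ALT, general cardiac, other (3) | Keep dose, silent on duration | 400 mg if prolonged, then 200 mg | Depends on reading |

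The table therefore keeps the dose or continues treatment in 6 of the 10 rows, reduces at once in 2 and holds first in 2.

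**Two cases.** A man has grade 2 CK elevation that persists from one weekly test to the next. Under the table he stays on 800 mg. Under the text, once the event counts as prolonged, he goes to 400 mg and then 200 mg. A second man has grade 2 neutropenia that resolves within 7 days. Under the table he is on 400 mg from onset. Under the text he stays on 800 mg unless those days count as prolonged.

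**How many men could be affected.** Table 1-2 gives, at 800 mg QD (n = 26), grade 1/2 muscle spasm in 9 and grade 1/2 CK increase in 6, the two most frequent events at that dose. Scaled to 11 men:

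- spasm: 11 x 9/26 = 3.8
- CK: 11 x 6/26 = 2.5

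Grades 1 and 2 are pooled and duration is not given, so the expected number with prolonged grade 2 lies anywhere from 0 to those figures. Purely as an assumption, a share of one quarter to one half gives 1.0 to 1.9 men for spasm and 0.6 to 1.3 for CK. The two groups may overlap and should not be added.

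**Whether the Gli1 effect can be sized.** Table 1-5 gives mean skin Gli1 inhibition of 75.6% at 200 mg (n = 4), 89.1% at 400 mg (n = 3) and 73.5% at 800 mg (n = 20). There is no dose ordering over the relevant range. As a bounding exercise, suppose k of 11 treated men are on a reduced dose and respond at rate q. The average treated rate is [(11 - k) x 0.70 + k x q]/11, and power is taken from a two-sided Fisher test at 0.10 against 10%, treating the arm as binomial at that average. With q = 0.70 there is no loss, and power is 0.88. With k = 4 and q = 0.10 the rate is 5.3/11 = 0.482 and power is 0.50. The documents supply neither k nor q, so this range shows only that the effect is unknown.

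**The case against.** The best defence is that the passages complement each other: the table gives the first response, and the text adds what happens if a grade 2 event persists. This is a fair reading of the AST/ALT, general cardiac and other-adverse-event rows, which say nothing about duration. A reader might infer that the table keeps the dose in those rows however long the event lasts; the table does not say so. The defence fails for CK, where the table covers the persistent case itself and keeps the dose through weekly tests until the grade falls.

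A second defence is that the table governs as the more specific source, since Section 5.1.3 refers to it for detail. Only one such table follows, so the wrong number is unlikely to mislead by itself. But no sentence gives the table precedence. If it overrode the text throughout, its row for all other adverse events would leave the general grade 2 rule almost nothing to cover. The table's status as a recommendation, and its footnote allowing case-by-case discussion, permit departures but do not rank the passages.

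Third, the hematologic conflict may rarely arise: Section 1.4.1 reports no treatment-related clinically significant hematology changes in phase I. That stands, and it is why CK and muscle events matter most here.

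Fourth, exposure is already measured. Dose changes go in the CRF, plasma LDE225 is assayed on the day of surgery (Section 6.2.3), and intra-prostatic levels are planned (Section 3.1). This also stands: new data collection is not needed.

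**Conclusion.** The inconsistency is real and lies in the current text. It is clearest for grade 2 CK elevation. It also holds for the trigger in the two hematologic rows and for the hold-first creatinine and bilirubin rows, and in weaker form for muscle pain or spasm. For the three rows that merely keep the dose it depends on the reading. The undefined term and the wrong table number add to it.

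At phase I rates about 3.8 of 11 men for spasm and 2.5 for CK would have the event at grade 1 or 2. This assumes that those rates, from 26 patients whose time on treatment may have differed from 4 weeks, carry over. How many would be prolonged grade 2 is not known.

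Two stronger conclusions are not supported. A reader might infer that the conflict biases or weakens the Gli1 result, since each man is 1/11 = 9.1 points of the treated-arm response rate. That matters only if the choice of passage changes his response status. All three skin means from 200 to 800 mg exceed the 50% threshold, skin is not prostate, and with a median effective half-life of 19 days (Section 1.4.2) a late reduction may change exposure little. A reader might also infer that the tolerability results become uninterpretable. Dose reductions are not among the endpoints listed in Section 2, and they are recorded; they would only be harder to compare between men.

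**What to change.** - Reconcile the grade 2 text of Section 5.1.3 with the grade 2 rows of Table 5-1, including the 1.5-3 x ULN rows, so that one rule applies to each toxicity.
- If the notion of a prolonged event is kept, give it a length.
- Correct the reference to Table 5-3, and state which passage governs if they still differ.
- In the analysis plan, use the dose history already recorded and the plasma and tissue drug levels at surgery as descriptors alongside each man's Gli1 change.

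Which rule is right is a clinical decision, and none is proposed here. The cost is amendment wording and a short descriptive listing; no new data, visits or patients are needed, and the sample size is unaffected.
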